9.6 Monitoring for Toxicity

“Toxic events” will be defined as one in which a patient has two dose reductions and then experiences another significant toxicity as defined in Section 5.0, irrespective of attribution. A two-stage stopping rule will be used to monitor for an excessive number of these toxic events. All patients described below must be evaluable for toxicity. All patients who receive at least one dose of Pegylated interferon will be evaluable for toxicity. A review of treatment feasibility and patient safety will be undertaken if we observe at least 2/9 or 4/17 toxic events. The rule will be met about 4% of the time if the true incidence of toxic event is 10%, and 90% of the time if the true incidence is 30%.

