2.5 Clinical Data of Interferon in Cancer

2.5.1 Interferon and Gliomas: In gliomas, Nagai et al reported a partial response in 2 / 9 patients with glioblastoma treated with rIFN-alpha A, and 40% response rate (1 complete response, 7 partial responses) in 20 patients with glioblastoma treated with human fibroblast interferon-beta. [10]

Two phase II trials of temozolomide with interferon alpha-2b (pegylated and non-pegylated) in patients with recurrent glioblastoma multiforme demonstrated PFS at 6 months was 31% for 29 evaluable patients in the IFN study and 38% for 26 evaluable patients in the PEG group. In recurrent GBM patients, in combination with both studies of standard dose TMZ with either IFN or PEG showed improved efficacy when compared to reports using TMZ alone. The grade 3 or 4 toxicities more common were leucopenia and thrombocytopenia. Grade 3 or 4 fatigue occurred in 18% of patients on both studies. Lymphopenia was not seen frequently. [11]

In a pediatric study involving children with recurrent malignant tumors treated with recombinant interferon- β , 2 of 9 children with brainstem gliomas had a partial response (>50% reduction in tumor size) and 2 children had prolonged disease stabilization (1 child for 3.5 years).[12]

In a follow-up study of pediatric patients with brainstem gliomas treated with IV recombinant β -interferon during hyperfractionated radiation therapy, 13 of 32 patients required dose modifications due to hepatic or hematologic toxicity. [13]

The optimal dosing for interferon alpha has not yet been established, although it has been used to treat a variety of neoplasms. It has traditionally been administered in high doses = 3,000,000 U/m², 2-3x/week. Significant side effects have limited its use.

In one study in which interferon alpha-2a was administered to pediatric patients with recurrent or progressive craniopharyngiomas at a dose of 8,000,000 U/m² daily for 16 weeks, followed by the same dose 3 times a week for an additional 32 weeks, the need for radiation therapy was significantly delayed in 6 of 15 patients, but more than 50% of the patients experienced significant toxicity requiring intervention or dose reduction within the first 8 weeks of therapy. [14]

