5.1 Non-hematological Toxicities

The dose of Pegylated interferon will be reduced for any of the following toxicities at least possibly attributed to Pegylated interferon

- Any Grade 4 non-hematological toxicity
- Any Grade 3 non-hematological toxicity with the specific exclusion of:

- Grade 3 nausea and vomiting controlled by antiemetics
- Grade 3 fever or infection
- Grade 3 fever, myalgias, arthralgias, and rigors.
- Grade 3 hypophosphatemia, hypokalemia, hypocalcemia or hypomagnesemia responsive to oral supplementation.

- Any Grade 2 non-hematologic toxicity that persists for > 3 days and is considered sufficiently medically significant or sufficiently intolerable by patients that it requires treatment interruption
- Any other adverse event attributed to Pegylated interferon that requires treatment interruption for > 3 days or which recurs upon drug re-challenge and requires treatment interruption.
- Non-hematological toxicity that causes a delay of more than 14 days between treatment cycles.

Patients who experience non-hematologic toxicity should have appropriate laboratory testing at least weekly until the toxicity has resolved.

If the toxicity does not return to less or equal than Grade 1 within **14** days, the patient will no longer be eligible to receive treatment on this study.

If the toxicity returns to less or equal to Grade 1 within 14 days, the patient may restart the study drug at initial dose modification once weekly and remain at that dose.

If the same Grade 3 or 4 non-hematologic toxicity recurs, hold drug and wait until toxicity returns to less or equal to Grade 1. If toxicity returns to less or equal to grade 1 within 14 days, the patient may restart the study drug at second dose modification and remain at that dose. If the toxicity does not return to less than Grade 1 within **14** days, the patient will no longer be eligible to receive treatment on this study.

If the same Grade 3 or 4 non-hematological toxicity recurs and it is felt to be due to the study drug, the patient will no longer be eligible to receive pegylated interferon alfa-2b.

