8.0 CRITERIA FOR REMOVAL FROM PROTOCOL THERAPY AND OFF STUDY CRITERIA

8.1 Criteria for Removal from Protocol Therapy

- Progressive disease (see definition in Section 10.4).
- Significant toxicity at least possibly attributed to Pegylated interferon despite two dose reductions (as stated in Section 5.0).
- Refusal of further protocol therapy by patient/parent/guardian.
- Completion of 26 cycles of protocol therapy.
- Physician determines it is in patient's best interest.
- Development of a second malignancy.
- Patient becomes pregnant while on study.

Patients who are off protocol therapy are to be followed until they meet the criteria for Off Study (see below). Follow-up data will be required unless consent was withdrawn.

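### The Section 9.6 toxicity trigger leaves out patients whose treatment ends for toxicity before a second dose reduction, although they stay in its denominator

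*Combined protocol and SAP*

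**What the plan says.** - **Section 9.6, event.** A toxic event is "one in which a patient has two dose reductions and then experiences another significant toxicity as defined in Section 5.0, irrespective of attribution".
- **Section 9.6, trigger.** "A review of treatment feasibility and patient safety will be undertaken if we observe at least 2/9 or 4/17 toxic events".
- **Section 9.6, denominator.** "All patients who receive at least one dose of Pegylated interferon will be evaluable for toxicity".
- **Section 9.6, stated performance.** "The rule will be met about 4% of the time if the true incidence of toxic event is 10%, and 90% of the time" at a true incidence of 30%.
- **Section 5.1, early exit.** When a non-hematologic toxicity has not settled to Grade 1 or lower after 14 days, the stated consequence is that "the patient will no longer be eligible to receive treatment on this study". Treatment resumes at the first modified dose only if the toxicity settles in that time. After a recurrence, the second modified dose is likewise conditional on recovery within 14 days, and failure to recover again ends treatment.
- **Sections 5.0 and 8.1.** Both provide for removal when toxicity continues after two reductions, which matches the 9.6 event. Section 8.1 does not list the 14-day exit. It does list "Refusal of further protocol therapy by patient/parent/guardian" and physician judgement.
- **Section 9.8.** The number of patients coming off therapy because of toxicity is summarised descriptively, with no threshold.

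**The concern.** The monitored event is the end of one path: toxicity, reduction, toxicity, second reduction, toxicity. The protocol prescribes shorter paths that also end treatment for toxicity, and a patient on one of them can never satisfy the 9.6 definition. Having had at least one dose, that patient still counts in the 9 or the 17 as someone without a toxic event.

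The counts of 2/9 and 4/17 are the only numerical safety boundary short of a toxic death. If a sizeable share of treatment-ending toxicity takes the shorter paths, the boundary is insensitive to the outcome it is meant to detect. The trial treats children and young adults for up to two years, so how often the drug has to be stopped for toxicity is central to the feasibility and safety review that 9.6 describes.

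**Working it through.** **Step 1. Which exits are counted**

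| Route off treatment | Reductions taken | Counted in 9.6? |
|---|---|---|
| Further significant toxicity after two reductions (5.0, 8.1) | 2 | Yes |
| First non-hematologic toxicity, not recovered in 14 days (5.1) | 0 | No |
| Recurrent non-hematologic toxicity, not recovered in 14 days (5.1) | 1 | No |
| Refusal or physician decision because of toxicity (8.1), before a second reduction | 0 or 1 | No |

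Counting the instruction to reduce as a reduction, whether or not the lower dose was given, would not rescue the first-occurrence case: that makes one, not two. Section 5.2 has no 14-day exit, so the 5.1 part of the gap concerns non-hematologic toxicity only.

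**Step 2. The plan's own figures**

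Inputs from 9.6: 9 patients, then 8 more; review if at least 2 of 9 or at least 4 of 17. With per-patient probability q of a counted event, X9 the count in the first 9 and X8 the count in the next 8:

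P(met) = P(X9 ≥ 2) + P(X9 = 0) × P(X8 ≥ 4) + P(X9 = 1) × P(X8 ≥ 3)

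- q = 10%: 0.2252 + 0.3874 × 0.0050 + 0.3874 × 0.0381 = 0.242. The plan says about 4%.
- q = 30%: 0.8040 + 0.0404 × 0.1941 + 0.1556 × 0.4482 = 0.882. The plan says 90%.

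Other readings of the rule do not recover the stated pair. At 10% and 30% respectively:
- 2/9 alone: 22.5% and 80.4%
- 4/17 alone: 8.3% and 79.8%
- both thresholds required: 6.6% and 72.0%
- thresholds read as strictly more than (at least 3/9 or 5/17): 6.2% and 68.9%

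The misstated 4% is a separate error. It matters here because the figures must be recomputed once the event changes.

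**Step 3. Effect of the uncounted routes**

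The documents do not say what share f of treatment-ending toxicity leaves uncounted, so f is varied over its whole range. If a proportion p of patients has treatment-ending toxicity, the countable rate is q = p × (1 − f).

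Example, p = 30% and f = 50%: q = 15%, and P(met) = 0.4005 + 0.2316 × 0.0214 + 0.3679 × 0.1052 = 0.444.

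| f | P(met), p = 30% | P(met), p = 40% |
|---|---|---|
| 0% | 88.2% | 97.5% |
| 25% | 71.3% | 88.2% |
| 50% | 44.4% | 63.3% |
| 75% | 15.0% | 24.2% |
| 100% | 0% | 0% |

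The fair comparator is the f = 0 row. The plan's 90% refers to a 30% incidence of the 9.6 event itself and is not quite what the rule delivers.

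**The case against.** The strongest reply is that 9.6 is one layer of several. Section 11.2 defines life-threatening events, among others, as serious. Such events go to the clinical trials coordinator within 24 hours, and the coordinator notifies the DSMB. The DSMB meets regularly and can recommend changing the study. Section 9.7 deals with toxic death, and Section 9.8 tabulates removals for toxicity. The 9.6 event also mirrors the one explicit toxicity criterion in 8.1, so it was not chosen arbitrarily.

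This stands in part. A reader might infer that a run of early removals would go unreviewed; the documents do not support that. Events meeting an SAE criterion would reach the DSMB. What is missing is a pre-set count that obliges a review.

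Three other stronger readings also fail:

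- **That the rule omits the most severe toxicity.** The 14-day exit selects persistent toxicity. A Grade 4 event that settles quickly can be re-dosed, and 5.1 also covers some Grade 2 toxicity that persists and requires interruption.
- **That no counted event can occur before the third cycle.** Section 5.0 ties reductions to subsequent cycles, but 5.1 allows a restart on recovery within 14 days without tying it to a new cycle.
- **That the background data show early exits will be common.** Section 2.5 reports that "more than 50% of the patients experienced significant toxicity requiring intervention or dose reduction within the first 8 weeks of therapy", but for interferon alpha-2a at 8,000,000 U/m² daily, and it counts intervention or dose reduction rather than failure to recover. Section 2.6 gives 1 dose-limiting toxicity in 12 patients on this drug at 1.0 µg/kg.

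**Conclusion.** The gap is established by the text alone: Section 5.1 ends treatment for toxicity in patients whom Section 9.6 cannot count, and no other section gives them a numerical trigger. The same holds for toxicity-driven exits under 8.1 before a second reduction.

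Its size is not established. At 30% treatment-ending toxicity, the chance of meeting the rule runs from 88.2% with no uncounted exits to 0% if all are uncounted. The 44.4% at an even split is one point in that range, not an estimate. The calculation assumes independent patients with a common event probability, and full follow-up of 9 and then 17.

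This should be fixed, but it is not a failure of safety oversight as a whole, because SAE reporting, DSMB review, the toxic-death rule and the descriptive summary remain in place.

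**What to change.** In Section 9.6, extend the toxic event to include permanent discontinuation of study drug for toxicity at any dose level. That would cover removal under 5.1 for failure to recover within 14 days, and refusal or physician withdrawal where toxicity is the recorded reason. Keep the present definition as the other limb.

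Three things go with it:

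- **Reconcile 9.6 with 5.0, 5.1 and 8.1**, so that the removal routes and the monitored event agree. No dosing or removal rule needs to change for this.
- **State how attribution applies.** The present event disregards attribution, whereas 5.1 requires at least a possible link and the added limb depends on a recorded toxicity reason.
- **Restate the operating characteristics** for the rule finally used. If 2/9 and 4/17 are kept, the figures are about 24% at 10%, 63% at 20% and 88% at 30%, where the incidence is that of the broader event.

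The cost is a short amendment to 9.6, a recalculation, and a toxicity reason recorded for refusals and physician withdrawals, which 9.8 does not explicitly require. The review will be triggered more often, but under 9.6 it is a review and not an automatic stop.

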9.0 STATISTICAL CONSIDERATIONS

9.1 Sample Size and Study Duration

This study will enroll patients without NF-1 and patients with NF-1. Based on the established accrual goals and incidence of pediatric low grade gliomas 17 patients can be accrued within 36 months of protocol activation, given an average of 1 patient per 2.1 months. Assuming 15% of patients are not evaluable or eligible, 20 patients total will be required to be enrolled on this study.

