9.8 Analysis of Toxicity

Estimates will be obtained using life-table methods, with an event defined as the first occurrence of a primary toxicity. Time scale used in the time to first occurrence of a key acute and subacute toxicity is time in days since the start of therapy. Patients who have progression or recurrence of disease will be censored in these analyses. The rates of individual toxicities in each course of treatment, the number of patients who require a dose reduction and number of patients who come off protocol therapy due to toxicity will be summarized using standard descriptive statistical methods. To evaluate hematologic toxicity of long term Pegylated interferon administration adverse event data will be collected using CTCAE version 5.0 toxicity coding. Grade 3 or greater hematologic toxicities will be recorded per reporting period.

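### The toxicity review rule in Section 9.6 is met about 24% of the time at a 10% event rate, not the stated 4%

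*Combined protocol and SAP*

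**What the plan says.** Section 9.6 introduces the rule this way: "A two-stage stopping rule will be used to monitor for an excessive number of these toxic events". The action it sets out is a review: "A review of treatment feasibility and patient safety will be undertaken if we observe at least 2/9 or 4/17 toxic events". The closing sentence gives the rule's operating characteristics. The first is "The rule will be met about 4% of the time if the true incidence of toxic event is 10" per cent; the second is 90% at a true incidence of 30%.

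The looks match the efficacy stages in Sections 9.2 and 9.5, which are 9 patients and then 8 more, 17 in total. The toxicity population is wider than the efficacy one: "All patients who receive at least one dose of Pegylated interferon will be evaluable for toxicity". Section 9.1 allows for non-evaluable or ineligible patients, so that "20 patients total will be required to be enrolled on this study".

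**The concern.** Two or more events among 9 patients is not a rare result when each patient has a 10% chance of an event: the expected count is already 0.9. A rule that can be met on that result alone should not have a 4% chance of being met.

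Section 9.6 is the plan's only numerical boundary for non-fatal toxicity, and these two probabilities are the only properties given for it. Someone relying on the 4% would read 2 events in the first 9 patients as strong evidence that the incidence exceeds 10%, and might have accepted the boundaries for that reason. Whoever conducts the review needs to know how often the rule is met when the true rate is 10%.

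**Working it through.** **Inputs, from Sections 9.5 and 9.6.** Looks at 9 and 17 patients (9 + 8). Review if X1 ≥ 2 in the first 9, or if the cumulative count X1 + X2 ≥ 4 in 17. True incidence p = 0.10 or 0.30. X1 ~ Bin(9, p) and X2 ~ Bin(8, p), independent, with all 17 patients treated.

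**Formula.**

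P(rule met) = P(X1 ≥ 2) + P(X1 = 0)·P(X2 ≥ 4) + P(X1 = 1)·P(X2 ≥ 3)

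**At p = 0.30 (stated 90%).**
- P(X1 = 0) = 0.7^9 = 0.0404; P(X1 = 1) = 9 × 0.3 × 0.7^8 = 0.1556; P(X1 ≥ 2) = 0.8040
- P(X2 ≥ 4) = 0.1941; P(X2 ≥ 3) = 0.4482
- Total = 0.8040 + 0.0404 × 0.1941 + 0.1556 × 0.4482 = 0.8040 + 0.0078 + 0.0698 = **0.8816**

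This agrees with the plan's 90% to within two percentage points.

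**At p = 0.10 (stated 4%).**
- P(X1 = 0) = 0.9^9 = 0.3874; P(X1 = 1) = 9 × 0.1 × 0.9^8 = 0.3874; P(X1 ≥ 2) = 0.2252
- P(X2 ≥ 4) = 0.0050; P(X2 ≥ 3) = 0.0381
- Total = 0.2252 + 0.3874 × 0.0050 + 0.3874 × 0.0381 = 0.2252 + 0.0019 + 0.0148 = **0.2419**

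The plan's 4% is not reproduced: 24.2 / 4 is about 6. A simulation of 2,000,000 trials gave 0.2420 at 10% and 0.8814 at 30%.

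**Other readings of the rule.** None gives about 4% together with about 90%.

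| Reading | p = 0.10 | p = 0.30 |
|---|---|---|
| As written: ≥2/9 or ≥4/17 | 24.2% | 88.2% |
| First look only, ≥2/9 | 22.5% | 80.4% |
| Final look only, ≥4/17 | 8.3% | 79.8% |
| Both looks required | 6.6% | 72.0% |
| More than 2/9 or more than 4/17 | 6.2% | 68.9% |
| ≥2/9, or ≥4 among the 8 new patients | 22.9% | 84.2% |
| ≥2/9 or ≥4/20 (all planned enrolments) | 26.7% | 92.8% |

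**Could a boundary be misprinted?** All boundary pairs with looks at 9 and 17 were searched, including pairs in which one look can never trigger.
- With at most 5% at p = 0.10, the highest probability at p = 0.30 is 62.1% (4/9 or 5/17, which gives 2.5% at p = 0.10).
- With at least 90% at p = 0.30, the lowest probability at p = 0.10 is 23.8% (3/17, with no lower first-look limit).

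So no rule of this form on these looks has the 4% and 90% properties together.

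**Where the written rule does give 4%.** Solving for p gives a true incidence of 3.6%.

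**The case against.** The strongest reply is that little follows in practice. The boundaries are clear, meeting them leads to a review, detection at 30% is nearly as stated, and no efficacy decision depends on the figure. That is fair, and it limits the seriousness of the point. It does not make the sentence true. Section 9.6 also calls the procedure a stopping rule while describing only a review, so the mild consequence depends on the review wording being what operates.

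A second reply is that 24.2% and 88.2% assume all 17 patients are treated. Under Section 9.2 the trial ends after 9 patients if none responds, with probability 0.95^9 = 0.630 at a 5% response rate and 0.75^9 = 0.075 at 25%. The second toxicity look then does not occur. Assuming that response and toxicity are independent, which the plan does not state:
- 5% response rate: 0.2252 + 0.370 × 0.0167 = 23.1% at p = 0.10; 0.8040 + 0.370 × 0.0776 = 83.3% at p = 0.30.
- 25% response rate: 24.1% and 87.6%.

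This stands as a qualifier. The 10% figure barely moves, but the 30% figure can be nearly 5 points lower, so the corrected sentence should state its condition.

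Third, the plan calls 10% and 30% reference incidences only and labels neither acceptable nor unacceptable. That is correct, and nothing here needs the label: the plan attaches a probability to p = 0.10, and the probability is wrong. Which patients count as having a toxic event is a separate design choice and is not in question.

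**Conclusion.** The concern holds. At a true incidence of 10% the rule in Section 9.6 is met 24.2% of the time against a stated 4%, and 22.5 of those percentage points come from the first look. At 30% it is met 88.2% of the time, consistent with the stated 90%. The calculation uses only the boundaries and incidences in Section 9.6 and the stage sizes in Section 9.5. It assumes independent patients with a common event probability and, for these exact figures, that all 17 are treated. Early closure for lack of response leaves the 10% figure at 23% or more.

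The consequence is a misdescribed safety rule and more frequent reviews than readers would expect, not missed toxicity. It should be corrected, but it does not threaten the trial's conclusions.

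**What to change.** Replace the last sentence of Section 9.6 with figures that belong to the stated rule. For example: if all 17 patients are treated, the rule will be met about 24% of the time when the true incidence of toxic events is 10%, and about 88% of the time when it is 30%. In the same edit, make clear whether meeting the rule leads to a review or to stopping, since the section uses both descriptions.

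This is a wording change with no added patients or procedures. Its only cost is that the stated trigger rate at 10% becomes less favourable.

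If the team wants the rule met less often at 10%, it should choose new boundaries and report their exact properties. That costs detection: 3/9 or 4/17, for instance, gives 10.2% at an incidence of 10% and 81.3% at 30%. The 4% and 90% pair should not be kept as a target, because no boundaries on looks at 9 and 17 patients achieve it.

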9.7 Interim Monitoring of Toxic Death

Toxic death is death predominantly attributable to treatment-related causes. The occurrence of toxic death at any time will be a primary endpoint for safety monitoring. Any toxic death on study will be reviewed with DSMB prior to continuing enrollment on study. The study will be stopped if there is one toxic deaths on study.

9.8 Analysis of Toxicity

Estimates will be obtained using life-table methods, with an event defined as the first occurrence of a primary toxicity. Time scale used in the time to first occurrence of a key acute and subacute toxicity is time in days since the start of therapy. Patients who have progression or recurrence of disease will be censored in these analyses. The rates of individual toxicities in each course of treatment, the number of patients who require a dose reduction and number of patients who come off protocol therapy due to toxicity will be summarized using standard descriptive statistical methods. To evaluate hematologic toxicity of long term Pegylated interferon administration adverse event data will be collected using CTCAE version 5.0 toxicity coding. Grade 3 or greater hematologic toxicities will be recorded per reporting period.

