1.2 SECONDARY STUDY OBJECTIVES

1.2.1

To estimate event free survival (EFS) (based on standard two or three-dimensional tumor measurements) for children with recurrent, refractory or progressive Juvenile Pilocytic Astrocytomas and Optic Pathway Gliomas who are treated with Peginterferon.

1.2.2

To define the toxicities of long term weekly pegylated interferon alpha-2b in pediatric patients with refractory, recurrent and progressive Juvenile Pilocytic Astrocytomas and Optic Pathway Gliomas.

1.2.3

To compare response categories and EFS across the 3 MR sequences (T2-weighted, FLAIR, T1-weighted post-contrast).

1.2.4

To evaluate the quality of life for patients with recurrent, refractory and progressive Juvenile Pilocytic Astrocytomas and Optic Pathway Gliomas who receive therapy with pegylated interferon alpha-2b

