4.3 Pegylated interferon Administration

Pegylated interferon will be administered weekly (**+/- 5 days**) at a dose of 1mcg/kg/dose via subcutaneous injection, approximately at the same time every week.

It is important to rotate the injection sites. Teaching will be done to the parents/guardian/patient in the first and/or second injection so the family will learn the technique and can continue to do it at home. Family/guardian will be provided with diaries to document compliance and side effects.

Patients may be pre-medicated with acetaminophen or ibuprofen. Specifically, patients can receive acetaminophen 10-15 mg/kg (maximum 650 mg per dose, maximum dose 4 grams/24 hours) or ibuprofen 10 mg/kg within 1 hour prior to receiving PEPegylated interferon. The patients can continue on either acetaminophen or ibuprofen for up to 48 hours after the pegylated interferon injection as needed. The maximum dose of ibuprofen in a 24-hour period will be 40 mg/kg or patients with weight for more than 45 kg is 2.4 grams/24 hours. Premedication is optional.

Pegylated interferon will begin a Cycle on Day 1 if **ANC \geq 1,000/ μ L, platelet count \geq 100,000/ μ L** (transfusion independent).

Dose calculations should be based on actual weight and adjusted as necessary prior to each cycle.

The maximum dose is 150 mcg.

Note: The calculated dose should be rounded to the nearest highest 5mcg of the prescribed dose for convenience of administration. Each cycle is 28 days. The total duration of the trial is 2 years a total of 26 cycles.

See Section 5.0 for Dose Modifications Based on Toxicities.

The therapy delivery maps (TDMs) for this cycle are on the next pages

Following completion of the first cycle, the Pegylated interferon cycle is repeated weekly for up to a total of 26 cycles, as tolerated and in the absence of disease progression (see Section 10.4 for Response Evaluation). If disease progression occurs, the patient will be taken off protocol therapy.

Subsequent Pegylated interferon cycles should begin on Day 29 or when ANC \geq 1,000/ μ L, platelet count \geq 100,000/ μ L (transfusion independent), whichever occurs later.

Therapy Delivery Plan

Pegylated interferon Dose 1mcg/kg/dose 4 consecutive weeks (28 days) will constitute one cycle. This therapy delivery map relates to all cycles of Pegylated interferon
	
Patient Name: _____ DOB _____

--	---

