4.4 Criteria for Starting Subsequent Courses of Treatment

A course may be repeated every 28 days, up to a total of 2 years if the patient has at least stable disease and has again met laboratory parameters.

Patients who complete a treatment cycle may receive another cycle if:

- Disease Status: the patient has no evidence of progressive disease or in the opinion of the investigator, the patient is benefiting from the therapy with pegylated interferon alfa-2b) as evidenced by a decrease in tumor-related symptoms.
- Toxicity: the patient has not experienced any toxicity that meets off-study criteria as described in Section 5.0
- Patients will not be allowed to have a dose escalation after dose reduction due to toxicity.

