10.3 Tumor measurement

Given the complexity of JPA/ OPG, the tumor size/response will be assessed in different segments:

1. Optic nerve (right, left)

2. Chiasm /hypothalamus
3. Brain parenchyma / retrochiasmatic visual pathways (optic tracts, optic radiations, internal capsule, posterior fossa) (right/left).

Therefore, up to 5 measurements may be necessary.

1. Longest diameter of target lesion(s) measured from the axial plane or the plane in which the aspect of the tumor is best seen or measured, provided the same plane is used in follow ups.
2. The longest measurement of the tumor (or width, W) should be determined.
3. The perpendicular measurements (transverse (T) measurement-perpendicular to the width in the selected plane. The length (L) – tumor extent in the plane perpendicular to the selected plane will not be used for measurement purpose.
4. The lower limit of the target lesion(s) should be at least twice the thickness of the slices showing the tumor to decrease the partial volume effect (e.g. 8 mm lesion for a 4 mm slice).
5. An automated tool (OncoTreat) will be employed to evaluate how the values obtained with this tool compare with the manually derived values. The manually derived values will be the measurements used for the study.

10.4 Determination of tumor progression/response.

Progressive disease

Any patient with clinical or radiographic evidence of progressive disease following any treatment cycle will no longer receive pegylated interferon alfa-2b (see Section 5.1). Radiographic progression is defined as appearance of new tumors or an increase in any previously measurable lesion by $\geq 25\%$ in the product of the two longest perpendicular diameters or by 40% in the product of the three diameters. The preferred method for tumor measurement is to use the 3 diameters when available.

If possible, tumor progression should be documented by the appropriate radiological study. For patients who develop worsening neurological symptoms, attempts should be made to distinguish progressive disease from other causes prior to removing the patient from the study

Determination of tumor response or progression will be based on the pre-study baseline scan performed closest to time of study entry. Progressive disease will be defined based on the comparison of the baseline scan to the scan demonstrating best response.

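### The section 9.8 toxicity life table censors at progression, so it tends to overstate the proportion of treated children with an on-treatment toxicity (minor)

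*Combined protocol and SAP*

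**What the plan says.** Section 9.8 of the combined protocol and SAP sets the estimator: "Estimates will be obtained using life-table methods, with an event defined as the first occurrence of a primary toxicity". The clock is "time in days since the start of therapy", and the sentence that sets it refers to key toxicities of the acute and subacute kind. Then: "Patients who have progression or recurrence of disease will be censored in these analyses". The same section also plans descriptive summaries: toxicity rates in each course, the number of patients needing a dose reduction, and the number leaving therapy because of toxicity.

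The related objective, 1.2.2, is "To define the toxicities of long term weekly pegylated interferon alpha-2b" in children with refractory, recurrent and progressive tumours.

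Three places say that progression ends the drug:
- Section 4.3: "If disease progression occurs, the patient will be taken off protocol therapy".
- Section 8.1: progressive disease is the first listed criterion for removal from protocol therapy.
- Section 10.4: "Any patient with clinical or radiographic evidence of progressive disease following any treatment cycle will no longer receive pegylated interferon alfa-2b".

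Section 4.4 reads differently. It allows another cycle if there is no progression, or if "in the opinion of the investigator, the patient is benefiting from the therapy with pegylated interferon alfa-2b".

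The documents name no cumulative-incidence or competing-risk method. They do not describe the life table as a risk that supposes no progression, they do not define primary toxicity, and they give no expected toxicity or progression rate for this trial.

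**The concern.** A child taken off pegylated interferon at progression can no longer have a new on-treatment toxicity. Censoring assigns that child the same future toxicity risk as the children still on drug. One minus the life table therefore answers the question of what the toxicity risk would be if no child progressed. A reader of the trial report is likely to take the curve as the share of treated children who had the toxicity, and the plan says nothing to prevent that. In a trial of refractory and progressive disease, many children may leave treatment through progression. The share read off the curve would then be too high, by an amount that grows with follow-up for as long as new toxicities keep appearing.

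**Working it through.** **No figure to reproduce.** The plan states no toxicity proportion, progression rate or precision for this life table. The direction can be proved; the size can only be illustrated.

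**Direction.** Let h(u) be the rate of first toxicity among children on drug and progression-free. Let S_T(u) be the survival curve built from h alone, and S_P(u) the corresponding curve for progression.
- Life table: 1 − S_T(t) = ∫ S_T(u) h(u) du.
- Cumulative incidence with progression competing: ∫ S_T(u) S_P(u) h(u) du.

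S_P(u) is at most 1, so the second integral cannot exceed the first. They are equal only if no progression precedes any of the toxicity risk.

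A small example: 8 of 17 children progress without toxicity, then one of the remaining 9 has the first event. The life table gives 1/9 = 11.1%; the share of treated children is 1/17 = 5.9%.

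**Inputs for size.**
- Horizon: 2 years (26 cycles of 28 days, section 4.3).
- Toxicity hazard: 0.35 per year. This is an assumption.
- Progression hazard: section 2.2 cites a vinblastine trial in recurrent or refractory low-grade glioma with 5-year PFS of 42.3%. Under a constant hazard, −ln(0.423)/5 = 0.172 per year, which means 1 − 0.423^(2/5) = 29% progressing by 2 years. Carrying this over to the present trial is also an assumption.

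**Toxicity spread evenly over 2 years.**
- Life table: 1 − exp(−0.35 × 2) = 50.3%.
- Cumulative incidence: 0.35/(0.35 + 0.172) × [1 − exp(−0.522 × 2)] = 0.670 × 0.648 = 43.4%.
- Gap: 6.9 points.

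**Toxicity confined to the first 3 months**, with progression at a constant hazard. For a life-table value of 30%:

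| Progressing by 2 years | Cumulative incidence | Gap (points) |
|---|---|---|
| 29% | 29.4% | 0.6 |
| 50% | 28.8% | 1.2 |
| 70% | 28.0% | 2.0 |

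The largest early-toxicity case examined was a 50% life-table value with 70% progressing. It becomes 46.8%, a gap of 3.2 points. Section 7.1 puts the first response MRI at the end of cycle 3, so if progression were found only at scheduled scans the early gap would be close to zero.

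**Faster progression, toxicity spread evenly.** A life-table value of 30% at 2 years becomes 25.7% if 29% progress by then, 22.1% if 50% do, and 18.1% if 70% do.

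**Check at the trial's size.** In simulations of 17 patients with progression detected at 3-monthly scans, the mean life-table and crude on-treatment proportions were 30.2% and 26.3% (29% progressing), 30.1% and 23.2% (50%), and 30.2% and 19.6% (70%). The life table was never below the crude proportion in any run.

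**The case against.** Five points can be made for the plan.

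1. **The life table is aimed at early events.** Section 9.8 ties the time scale to acute and subacute toxicity, and the gap is then small. This largely stands. It does not remove the point: objective 1.2.2 concerns long-term treatment, section 2.3 lists longer-term effects such as depression and cognitive impairment, and primary toxicity is left undefined.

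2. **Risk while on drug and progression-free is a legitimate target.** This stands if censoring is independent. A cumulative incidence also has a drawback: the faster children progress off drug, the safer the drug looks. That supports showing both. The plan, however, does not say which quantity it intends.

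3. **Uncensored summaries are planned.** This is true, and they tell the reader something about treated children. They do not correct the curve.

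4. **Sampling error is larger.** With 17 patients, the standard error of a 43% proportion is about √(0.43 × 0.57/17) = 12 points, against a gap of 7. This is fair as to practical weight, but the gap is systematic and always in one direction.

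5. **Toxicity after progression is not counted.** Children continued under section 4.4 could have a first on-treatment toxicity after being censored. In the 30% examples with evenly spread toxicity, about 18% to 20% of progressed children would need a first toxicity after progression to cancel the overstatement. The one-sided direction therefore depends on progression actually ending treatment.

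A reader might infer a headline gap of 50% against 38%. That needs progression at 0.35 per year, a rate found nowhere in the documents and about twice that implied by the cited vinblastine trial. A reader might also infer that all long-term toxicity reporting is biased or that safety decisions are affected. Neither follows: sections 9.6 and 9.7 work on counts, and section 9.8 records grade 3 or greater hematologic toxicity separately for each reporting period.

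**Conclusion.** The point holds and is minor. Given that progression ends treatment, as sections 4.3, 8.1 and 10.4 say, one minus the section 9.8 life table never understates the proportion of treated children with an on-treatment toxicity, and it tends to overstate it. The size cannot be derived from the documents. The illustrations run from about 3 points or less for toxicity in the first 3 months to about 7 points at 2 years under an assumed toxicity hazard of 0.35 per year and the progression rate implied by the cited trial, and higher if progression is faster. The constant hazards are themselves an assumption. Only the life-table curve is affected, and its error is toward overstating harm. The fault is an unlabelled estimand that readers are likely to misread; the life table is not invalid for every purpose.

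**What to change.** In section 9.8:
- Make the main estimate the Aalen-Johansen cumulative incidence of first on-treatment toxicity, with progression, other removal from therapy and death as competing events.
- Keep the censored life table as a supplement, labelled as the risk while on drug and progression-free.
- Define primary toxicity, so that the event being estimated is fixed in advance.

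Reconcile section 4.4 with sections 4.3, 8.1 and 10.4 on whether treatment can continue after progression. The analysis needs that answer to know when on-treatment follow-up stops.

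The cost is a few sentences. The estimator is in standard software and uses the same data, and neither the sample size nor the stopping rules change.
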